- VRS pain scores, vital signs and medication side effects (e.g., ketamine-induced hallucinations) at 24, 48, and 72 hours following surgery; time to return of daily activities (oral diet, return of bowel function, ambulation, showering) in days, any complications such as cardiac arrhythmias, global evaluation of anesthesia experience with 0 = worst, 10 = best
- Length of hospital stay

V. 6 week post-surgical assessment data:

- VRS pain score, opioid/adjuvant consumption, medication side effects (e.g., hallucinations, constipation, nausea and vomiting), SF-12 score.

Note: all opioid consumption will be converted to morphine equivalents for data analysis and presentation.

DATA ANALYSIS

Sample size estimates were based on the test for inequality of opioid consumption among the methadone, ketamine, and ketamine + methadone groups. We expect to observe at least a 30% decrease in opiate consumption between ketamine + methadone group and methadone or ketamine. Prior studies demonstrated that the postoperative opioid consumption and its standard deviation for methadone and ketamine are quite similar (10, 21). Mean opioid consumption was approximately 67 mg \pm 38 mg (SD) for Menigaux's et al. ketamine group and median 63 mg (interquartile range, 27-86.1), which gives an estimated SD of 23. The expected group mean difference would be 18.9 for an approximate 30% decrease in opioid requirements. However, we would like to be more conservative in our study since the aforementioned study populations were most likely skewed. For a two-tailed hypothesis with alpha 0.05, we would need at least 38 subjects per group to achieve a power of 0.8 to detect a 30% reduction in opioid consumption.

Two group t-test of equal means (equal n's)

	1	2	3	4
Test significance level, α	0.050	0.050	0.050	0.050
1 or 2 sided test?	2	2	2	2
Group 1 mean, μ_1				
Group 2 mean, μ_2				
Difference in means, $\mu_1 - \mu_2$	18.900	20.000	17.000	15.000
Common standard deviation, σ	23.000	23.000	23.000	23.000
Effect size, $\delta = \mu_1 - \mu_2 / \sigma$	0.822	0.870	0.739	0.652
Power (%)	80	80	80	80
n per group	25	22	30	38

Similarly for VAS pain scores, previous studies found average scores to range from 2.8 ± 2.0 for methadone group and 5.4 ± 2.0 for the ketamine study (7, 10). With alpha 0.05, power 0.8 and mean difference of 1.6, each group needs at least 17 subjects to observe a 30% reduction in VAS pain scores.

Two group t-test of equal means (equal n's)

	1	2	3	4

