Test significance level, α	0.050	0.025	0.050	0.025
1 or 2 sided test?	2	2	2	2
Group 1 mean, μ_1				
Group 2 mean, μ_2				
Difference in means, $\mu_1 - \mu_2$	2.000	2.000	1.800	1.800
Common standard deviation, σ	2.000	2.000	2.000	2.000
Effect size, $\delta = \mu_1 - \mu_2 / \sigma$	1.000	1.000	0.900	0.900
Power (%)	80	80	80	80
n per group	17	21	21	25

Based on the power analysis, a sample size of 38 patients for each group will sufficiently allow us to detect at least a 30% reduction in postoperative opioid consumption and VAS pain scores with 80% power using a two sample t-test, significance level of 0.05 (two-sided). Total sample size will be 114.

ANOVA will be used to compare the continuous variables among the three treatment groups, and when significant differences are determined, a Newman-Keuls multiple-comparison test will be used to determine intergroup differences. Continuous data not normally distributed are analyzed by Kruskal-Wallis test, and when a significant difference is found, a Mann-Whitney U test is used for post-hoc comparisons between the intergroups. Chi-squared test (or Fisher's exact test) is used to analyze the categorical variables such as side effects and sex distribution.

INCLUSION & EXCLUSION CRITERIA

I. Inclusion criteria:

- 18 – 80 years old of either gender, scheduled for elective lumbar laminectomy

II. Exclusion criteria:

- ASA IV and above
- Intolerance, allergy, or contraindication to use of any medications used in this study
- Significant coronary artery disease (abnormal stress test, myocardial infarction within the last 3 months)
- Increased intraocular pressure (e.g., untreated glaucoma)
- Uncontrolled hypertension (BP > 140/90)
- Sleep apnea AND currently on continuous positive airway pressure (CPAP)
- Increased intracranial pressure or clinical signs thereof
- History of intracranial surgery, stroke, or brain aneurysm
- Cardiac arrhythmias particularly prolonged QT syndrome
- Drugs known to cause prolonged QT: class IA antiarrhythmics (quinidine, procainamide, dysopyramide), class III antiarrhythmics (sotalol, dofetilide, ibutilide, amiodarone), haloperidol, thioridazine, arsenic trioxide, HIV protease inhibitors, tricyclic antidepressants
- Individuals with significant psychological disorders including: schizophrenia, mania, bipolar disorder or psychosis
- Pregnant or lactating women
- Emergent laminectomy
- Those already receiving ketamine or methadone prior to surgery

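### The opioid SD of 23 mg behind the sample size does not follow from the quoted interquartile range (about 44 mg); 38 per group gives about 46–57% power for a 30% reduction, not 80%

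*Combined protocol and SAP*

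**What the plan says.** The DATA ANALYSIS section bases the sample size on opioid consumption, compared pairwise by a two-sample t-test. It draws on two earlier studies and describes their means and SDs as much alike.

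- For the cited ketamine study: "Mean opioid consumption was approximately 67 mg", with a reported SD of 38 mg.
- For the other source, which the sentence does not name: "median 63 mg (interquartile range, 27-86.1), which gives an estimated SD of 23".
- Target: "The expected group mean difference would be 18.9 for an approximate 30% decrease in opioid requirements". This is 30% of the 63 mg median.

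The plan then says it wants to be more cautious because the source populations were probably skewed. The opioid table shows differences of 18.9, 20, 17 and 15 mg, all at SD 23, giving 25, 22, 30 and 38 per group. The 15 mg column is adopted: "we would need at least 38 subjects per group to achieve a power of 0.8 to detect a 30% reduction in opioid consumption". The closing paragraph repeats the claim: "a sample size of 38 patients for each group will sufficiently allow us to detect at least a 30% reduction in postoperative opioid consumption", at 80% power, for a total of 114.

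**The concern.** An interquartile range covers about 1.35 SDs of a normal distribution, so an SD well below half the range's width cannot be right. Here the width is 59.1 mg, half of it is 29.6 mg, and the plan uses 23 mg. The value also conflicts with the plan's remark that the two studies agree: 38 and 44 are close, 38 and 23 are not. The only SD that was reported directly, 38 mg, appears in no column of the table.

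All 114 patients rest on this input. If it is too small, the power claimed for the opioid comparison is a property the design does not have. A non-significant opioid result could then be read as evidence that the combination spares no opioid, when the chance of detecting the planned effect was about even.

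**Working it through.** **Inputs (all from DATA ANALYSIS).** Two-sided alpha 0.05; power 0.80; n = 38 per group; equal allocation; two-sample t-test; target 18.9 mg; sizing difference 15 mg; SD used 23 mg; reported SD 38 mg; quartiles 27 and 86.1 mg, median 63 mg.

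**1. Reproducing the table.** Power comes from the noncentral t distribution with 2n − 2 degrees of freedom and noncentrality δ / (SD × √(2/n)). At SD 23, the smallest n reaching 80% power is:

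| Difference (mg) | Plan's n | Recomputed n |
|---|---|---|
| 18.9 | 25 | 25 |
| 20 | 22 | 22 |
| 17 | 30 | 30 |
| 15 | 38 | 38 |

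All four agree. The calculation is sound given SD 23, so the fault lies in that input.

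**2. What SD the quartiles imply.** Under normality each quartile lies 0.6745 SD from the median.

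- Full range: (86.1 − 27)/1.349 = 59.1/1.349 = 43.8 mg.
- Upper half only: (86.1 − 63)/0.6745 = 23.1/0.6745 = 34.2 mg.
- Lower half only: (63 − 27)/0.6745 = 36/0.6745 = 53.4 mg.

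None of these gives 23. The match with 86.1 − 63 = 23.1 suggests that the upper quartile distance was taken as the SD. That is an inference, and the conclusion does not depend on it.

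**3. Power with 38 per group for 18.9 mg.** √(2/38) = 0.2294; the critical t on 74 df is 1.993.

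| SD (mg) | Basis | Noncentrality | Power |
|---|---|---|---|
| 23 | plan | 18.9/(23 × 0.2294) = 3.58 | 94% |
| 34.2 | upper half of range | 2.41 | 66% |
| 38 | reported SD | 2.17 | 57% |
| 43.8 | full range | 1.88 | 46% |

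If 30% is taken of the 67 mg mean instead (20.1 mg), power is 62% at SD 38 and 51% at SD 43.8.

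**4. Does the step to 15 mg compensate?** With 38 per group, 80% power requires a standardised difference of about 0.651 (the plan's 15/23 = 0.652 gives 80.1%). For 18.9 mg that holds up to an SD of 18.9/0.651 = 29.0 mg, below 34.2, 38 and 43.8. For the 15 mg difference itself, power is 40% at SD 38 and 31% at SD 43.8. Also, 15 mg is 24% of 63 and 22% of 67, so the adopted column is not itself a 30% reduction.

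**5. What 38 per group can detect with 80% power.**

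- SD 38: 0.651 × 38 = 24.7 mg, which is 37% of 67 or 39% of 63.
- SD 43.8: 0.651 × 43.8 = 28.5 mg, which is 43% of 67 or 45% of 63.

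**6. n for 80% power at 18.9 mg.** 65 per group (195 in total) at SD 38; 86 per group (258 in total) at SD 43.8.

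**The case against.** The strongest reply has five parts.

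- *The range mixes sources.* The 46% comes from the interquartile range. The 57% pairs the other study's SD of 38 with a target taken from the 63 mg median. This is true, and each figure should carry its label. Pairing SD 38 with 30% of its own mean gives 62%, and the upper-half reading gives 66%. But 18.9 mg is the target the plan states, and no reading reaches 80%.
- *The data are skewed, so 43.8 is approximate.* This also stands. The quartiles lie 36 mg below and 23.1 mg above the median, and the plan itself mentions skew. The reported SD of 38 needs no such conversion, however, and skew is no reason for a smaller SD.
- *The planned analysis is not a t-test.* The plan specifies ANOVA with Newman-Keuls, or Kruskal-Wallis with Mann-Whitney for non-normal data. The power of the rank tests cannot be worked out from the figures given. The plan's own power claim is for a pairwise t-test, so it is checked on its own terms.
- *Opioid use is the secondary hypothesis.* BACKGROUND & SIGNIFICANCE puts pain scores first. On the plan's pain inputs (difference 1.6, SD 2.0), 38 per group gives 93% power. The consequence is therefore limited to the opioid endpoint. Still, STUDY OBJECTIVES names both outcomes in the first objective, and the sample size is explicitly based on opioid consumption.
- *The plan was deliberately cautious.* The step to 15 mg does give some protection, up to an SD of about 29 mg. Both source SDs exceed that.

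**Conclusion.** The concern holds. An interquartile range of 27–86.1 mg does not give an SD of 23 mg; it gives about 44 mg, and the directly reported SD is 38 mg. For the stated 18.9 mg target, 38 per group has about 57% power at SD 38 and 46% at SD 43.8. Even the most favourable quartile reading gives 66%. The 80% claimed twice in DATA ANALYSIS is not delivered on the plan's own source figures.

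This assumes one pairwise two-sample t-test at two-sided 0.05, a common SD, and complete data from all 38 per group. The 43.8 also assumes approximate normality. The total of 114 (3 × 38) contains no allowance for dropout. Losses, or an adjustment for several pairwise comparisons, would lower these figures further. The error must be corrected because the sample size rests on it.

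**What to change.** In DATA ANALYSIS:

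1. Replace the SD of 23 in the text and the opioid table with 38–44 mg, stating that 38 is reported and about 44 is derived from the interquartile range under normality.
2. Restate the power along these lines: with 38 per group and a pairwise two-sided t-test at 0.05, power for an 18.9 mg (30%) difference is about 57% at SD 38 and 46% at SD 44; the difference detectable with 80% power is about 25–29 mg (37–45%).
3. Correct the closing power sentence for opioid consumption to match.

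The cost is some wording and one table, and the stated power becomes less favourable. The correction does not in itself require a change in enrolment. Whether to accept the lower power or enlarge the trial is for the sponsor to decide; 80% power for 18.9 mg would take 65 (SD 38) to 86 (SD 43.8) per group, before any allowance for dropout.

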STUDY PROPOSAL

**Intraoperative Ketamine and Methadone for
Laminectomy: Effect on Recovery, Postoperative Pain,
and Opioid Requirements**

IRB #: Pro00030109

NCT02252432

Date: 02/15/2020

**Intraoperative Ketamine and Methadone for Laminectomy: Effect on Recovery,
Postoperative Pain, and Opioid Requirements**

IRB #: Pro00030109

PRINCIPAL INVESTIGATOR

[name]., Ph.D.

CO-INVESTIGATORS

[name] [name].

INSTITUTION

Department of Anesthesiology
Cedars-Sinai Medical Center
[name]
[name]

E-MAIL

[contact]

[contact]

[contact]

STUDY OBJECTIVES

1. To determine if intraoperative double NMDA antagonism with ketamine + methadone reduces postoperative pain scores and opioid consumption more than single NMDA antagonism with ketamine or methadone alone after lumbar laminectomy.
2. To compare the side effects and hospital course between post-laminectomy patients receiving intraoperative ketamine + methadone vs. ketamine or methadone alone.

BACKGROUND & SIGNIFICANCE

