Patients given methadone during anesthetic induction demonstrated a 50% reduction in opiate requirements and VAS pain scores at 48h post spine surgery, but not at 24 hours (11). Several prospective, randomized controlled studies have found that methadone was superior to morphine in duration of postoperative pain relief and opioid requirements. The methadone group averaged 20.7 hours of sustained post-surgical pain relief compared to 6 hours with morphine and required significantly less quantities (11.5 ± 8.5 mg vs. 41 ± 14.1 mg) (11). Similar studies have confirmed methadone's benefits (12, 13). Thus, ketamine may have maximum benefit in controlling postoperative pain and decreasing opioid-induced side effects the initial 24 hours while methadone can continue to provide pain relief for up to 48 hours. The use of methadone in perioperative pain management is frequently employed by anesthesiologists caring for patients undergoing spine surgery at our institution and is within the standard of care.

Although it is clear that ketamine and methadone both provide significant post-op pain relief and opiate-sparing effects for chronic pain patients, their combined effects remain largely unknown. We hypothesize that post-laminectomy patients who were administered intraoperative ketamine and methadone will have improved postoperative pain scores than those receiving intraoperative ketamine or methadone alone. As explained above, methadone, an opioid agonist weak NMDA antagonist, and ketamine, a strong NMDA antagonist, are individually effective for pain control via separate molecular pathways. We believe that the treatment of pain by two separate pathways will cause a synergistic effect greater than the pain control produced by either medication alone. Our secondary hypothesis is that following lumbar laminectomy, patients given intraoperative ketamine and methadone will require less opiates postoperatively than those receiving ketamine or methadone only.

SUMMARY OF STUDY DESIGN

The proposed study is a randomized, double-blinded, placebo-controlled evaluation of intraoperative ketamine and methadone on postoperative pain and opioid requirements for chronic pain patients undergoing lumbar laminectomy.

Three intervention groups will include:

1. Ketamine group: A bolus of intravenous (IV) ketamine during induction (0.5mg/kg), and an IV infusion of ketamine intraoperatively (5 mcg/kg/min)

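### The claim of 80% power for a 30% pain reduction with 38 per group holds against the plan's ketamine mean (94%) but not its methadone mean (44%); the text also pairs 17 per group with the wrong difference

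*Combined protocol and SAP*

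**What the plan says.** All the power figures are in DATA ANALYSIS.

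- **Opioid target.** "We expect to observe at least a 30% decrease in opiate consumption between ketamine + methadone group and methadone or ketamine". The opioid table ends at 38 per group for a difference of 15 with SD 23, and this sets the enrolment of 114.
- **Pain inputs.** The text goes on: "Similarly for VAS pain scores, previous studies found average scores to range from 2.8" (SD 2.0, methadone) up to 5.4 (SD 2.0, ketamine).
- **Pain sample size in the text.** At alpha 0.05 and power 0.8, with a "mean difference of 1.6, each group needs at least 17 subjects to observe a 30% reduction in VAS pain scores".
- **Pain table.** The differences are 2.0 and 1.8 points, each at alpha 0.05 and 0.025, with SD 2.0. The sizes are 17 and 21 per group for 2.0 points, and 21 and 25 for 1.8 points. There is no column for 1.6.
- **Conclusion.** 38 per group "will sufficiently allow us to detect at least a 30% reduction in postoperative opioid consumption and VAS pain scores with 80% power", by a two-sample t-test at two-sided 0.05. No comparator is named.

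Elsewhere, both single drugs are comparators for pain. The first item under STUDY OBJECTIVES asks whether the combination "reduces postoperative pain scores and opioid consumption more than single NMDA antagonism with ketamine or methadone alone". The hypothesis at the end of BACKGROUND & SIGNIFICANCE is that combination patients "will have improved postoperative pain scores than those receiving intraoperative ketamine or methadone alone". Lower opioid use is the secondary hypothesis.

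**The concern.** A percentage reduction becomes a difference in points only once a reference mean is fixed. For opioid use the plan treats the two single drugs as similar, so one difference can serve both comparisons. For pain its two reference means differ almost twofold (5.4 / 2.8 = 1.93), so one difference cannot. The 1.6 points in the text is 30% of the ketamine mean only, yet the conclusion is worded as if it covered every comparison.

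What is at stake is how a null result is read. Pain against each single drug is the first-stated hypothesis. A reader would take a non-significant pain comparison with methadone as coming from a test with 80% power for a 30% reduction. On the plan's figures, a true reduction of that size would be missed more often than found.

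Separately, the sentence giving 17 per group for 1.6 points disagrees with the table it introduces.

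**Working it through.** **Inputs, all from DATA ANALYSIS.** Two-sample t-test, two-sided alpha 0.05, n = 38 per group, SD 2.0, reference means 5.4 (ketamine) and 2.8 (methadone).

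**Method.** The standardised difference is d = (difference in means) / SD. Power comes from the non-central t distribution with 2n − 2 degrees of freedom and non-centrality d × √(n/2). The required n is the smallest whole number giving at least 80%.

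**Step 1: reproduce the plan's tables.** All eight columns come out exactly.

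| Table | Difference / SD | Alpha | Plan's n | Recomputed n |
|---|---|---|---|---|
| Opioid | 18.9 / 23 | 0.05 | 25 | 25 |
| Opioid | 20 / 23 | 0.05 | 22 | 22 |
| Opioid | 17 / 23 | 0.05 | 30 | 30 |
| Opioid | 15 / 23 | 0.05 | 38 | 38 |
| Pain | 2.0 / 2.0 | 0.05 | 17 | 17 |
| Pain | 2.0 / 2.0 | 0.025 | 21 | 21 |
| Pain | 1.8 / 2.0 | 0.05 | 21 | 21 |
| Pain | 1.8 / 2.0 | 0.025 | 25 | 25 |

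The method therefore matches the plan's, and the tables themselves are sound.

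**Step 2: power for a 30% pain reduction with 38 per group.**

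| Reference mean | 30% in points | d | Power at 38 | n per group for 80% |
|---|---|---|---|---|
| 5.4 (ketamine) | 0.30 × 5.4 = 1.62 | 0.81 | 93.6% | 25 |
| 4.1 (midpoint, an assumption) | 0.30 × 4.1 = 1.23 | 0.615 | 75.4% | 43 |
| 2.8 (methadone) | 0.30 × 2.8 = 0.84 | 0.42 | 43.9% | 90 |

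**Step 3: what 38 per group does detect.** At 80% power the smallest d is 0.651, so the difference is 0.651 × 2.0 = 1.30 points.

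- Share of the ketamine mean: 1.302 / 5.4 = 24%.
- Share of the methadone mean: 1.302 / 2.8 = 47%.
- The 30% claim is met only if the reference mean is at least 1.302 / 0.30 = 4.34.
- Against a mean of 2.8, it is met only if the SD is at most 0.84 / 0.651 = 1.29.

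**Step 4: the two headline powers are separate scenarios.** A 30% reduction from ketamine puts the combination at 5.4 − 1.62 = 3.78, which is above methadone's 2.8. A 30% reduction from methadone puts it at 2.8 − 0.84 = 1.96. That is 5.4 − 1.96 = 3.44 points below ketamine, where power exceeds 99.9%.

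**Step 5: the pain table against 30%.** 2.0 / 5.4 = 37% and 1.8 / 5.4 = 33%; 2.0 / 2.8 = 71% and 1.8 / 2.8 = 64%. No column is a 30% reduction from either mean.

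**Step 6: the pairing of 17 with 1.6.** d = 1.6 / 2.0 = 0.80. Power with 17 per group is 61.9%, and 80% needs 26. A one-sided test does not rescue it (73.8% with 17; 21 needed). With 38 per group, power at 1.6 points is 93.1%.

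**The case against.** The strongest reply is that the plan never sets a target of 0.84 points. Its only worded pain difference is 1.6, which is 30% of the ketamine mean, and 38 per group gives 93% power for it. The link to methadone comes from the opioid sentence and the word that opens the pain sentence, which may only introduce a second endpoint. This does not rescue the claim. The conclusion is not limited to ketamine, and the objective and hypothesis name both drugs for pain. If ketamine alone was meant, the plan needs to say so.

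Second, 2.8 is a weak anchor. It and 5.4 come from two different studies, no time point is given, and the plan does not predict that this trial's methadone arm will average 2.8. This stands as a limit: the 44% is conditional on that mean and on SD 2.0, and power would be 75% at the midpoint of the range. But 2.8 is the only methadone figure that the plan offers, and even the midpoint falls short of 80%.

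Third, sample size was set on opioid use and pain was only a check. That is true, and it is why enrolment is not in question. The separate 80% statement for pain still has to be right.

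Fourth, the no-30%-column remark is weak on its own, since 33% and 37% of 5.4 satisfy a target of at least 30%. It shows only that the table does not work out the stated case.

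Fifth, the planned analysis is ANOVA followed by Newman-Keuls, and the trial records a verbal rating scale while the power inputs are VAS scores. Both stand as cautions. In a simulation with normal data, SD 2.0 and equal single-drug means, a 1.3-point difference has about 75% power per comparison under that procedure. Any corrected sentence should therefore keep naming the t-test.

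**Conclusion.** The power claim for pain is wrong as written. On the plan's own means and SD, 38 per group gives 94% power for a 30% reduction from ketamine and 44% for a 30% reduction from methadone, which would need 90 per group. The two figures belong to different assumed combination means and should not be read as joint powers.

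The arithmetic is firm. The shortfall against methadone rests on a reference mean of 2.8 and SD 2.0; it disappears if the reference mean is about 4.34 or more, or if the SD is about 1.29 or less at a mean of 2.8.

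The pairing of 17 per group with 1.6 points is a minor slip with no effect on enrolment. The main point should be fixed because it governs how a null comparison with methadone would be interpreted.

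**What to change.** Reword two sentences in DATA ANALYSIS.

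1. **Conclusion after the pain table.** Replace the pain part with: *With 38 per group, a two-sample t-test at two-sided 0.05 has 80% power to detect a 1.3-point difference in pain score (SD 2.0). This is 24% of the ketamine reference mean (5.4) and 47% of the methadone reference mean (2.8); on these figures, 80% power for a 30% reduction is not provided against methadone.* If the 94% and 44% are quoted, add that they are separate scenarios with combination means of 3.78 and 1.96.
2. **Sentence before the pain table.** Change 17 to 26 for a 1.6-point difference, and say that 1.6 is 30% of the ketamine mean. If 17 is kept instead, change 1.6 to 2.0 and describe it as 37% of the ketamine mean.

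This adds no patients, visits or analyses. The only cost is a less favourable stated power for pain against methadone.

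### The 80% power stated for 38 per group belongs to a 15 mg difference (22–24%) in one t-test, not to the 30% reduction named in the text or to the planned three-group analysis

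*Combined protocol and SAP*

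**What the plan says.** All the sizing text is in the Data Analysis section of the combined protocol and SAP. It converts the target effect to milligrams: "The expected group mean difference would be 18.9 for an approximate 30% decrease in opioid requirements". The SD of 23 is attached to a "median 63 mg (interquartile range, 27-86.1), which gives an estimated SD of 23"; the ketamine source in the same sentence has a mean of 67 mg and an SD of 38 mg. After a remark that a more conservative approach is wanted because the source populations were probably skewed, the section concludes that "we would need at least 38 subjects per group to achieve a power of 0.8 to detect a 30% reduction in opioid consumption".

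The table that follows, for a two-group t-test at SD 23, lists differences of "18.900 20.000 17.000 15.000" and, in the same column order, "n per group 25 22 30 38". A closing statement repeats the claim for 38 per group, "with 80% power using a two sample t-test, significance level of 0.05 (two-sided").

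The next paragraph plans something else. Continuous variables are compared across three groups by ANOVA and, if that is significant, "a Newman-Keuls multiple-comparison test will be used to determine intergroup differences". Data that are not normally distributed go to Kruskal-Wallis and then Mann-Whitney. The first study objective asks whether the combination "reduces postoperative pain scores and opioid consumption more than single NMDA antagonism with ketamine or methadone alone".

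**The concern.** The power statement disagrees with the rest of the plan in three ways.

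- **Effect.** The text attaches 38 to a 30% reduction. The table attaches 25 to that reduction and 38 to a smaller one, and the text never names 15 mg as the design difference.
- **Test.** The power is for one two-sample t-test at 0.05. The analysis is a global test on three groups followed by a stepwise multiple-comparison procedure.
- **Claim.** Saying that the combination does better than ketamine or methadone alone would ordinarily rest on two comparisons. No power is given for winning both.

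A reader who later sees a difference from only one single drug, or from neither, will judge it against an 80% figure that describes neither the planned test nor the natural claim.

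**Working it through.** **Inputs, all from Data Analysis:** two-sided alpha 0.05; 38 per group; differences of 15 and 18.9 mg; SD 23 (used) and SD 38 (quoted for ketamine); reference consumption of 63 mg (median) and 67 mg (mean). Equal single-drug means are assumed for the joint power, because the section calls consumption in the two groups quite similar.

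**Step 1: reproduce the table.** The normal approximation is n = 2(1.960 + 0.842)² / (Δ/σ)². For 15 mg, Δ/σ = 15/23 = 0.652 and n = 36.9. The exact noncentral-t solution is 37.9, so 38. The other columns by noncentral t are 24.2 → 25 (18.9 mg), 21.8 → 22 (20 mg) and 29.7 → 30 (17 mg). All four match, so the table is sound and the fault is in the sentences around it.

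**Step 2: what 38 corresponds to.** 15/63 = 23.8% and 15/67 = 22.4%. The 30% effect is 18.9/63 = 30.0%, for which the table gives 25.

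**Step 3: power of one t-test at n = 38.** The noncentrality is (Δ/σ)√(n/2), with √19 = 4.359 and critical t(74) = 1.993.

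- 15/23: 0.652 × 4.359 = 2.84, power 80.1%
- 18.9/23: 0.822 × 4.359 = 3.58, power 94.2%
- 18.9/38: 0.497 × 4.359 = 2.17, power 57.1%

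**Step 4: power of the planned parametric procedure.** This was simulated with 400,000 normal trials per scenario, 38 per group, equal single-drug means and a pooled error with 111 degrees of freedom. The F-test is at 0.05. Newman-Keuls then tests the full range against q(3, 111) = 3.36 and an adjacent pair against q(2, 111) = 2.80. Winning both means that the combination is lowest and differs significantly from each single drug.

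| Difference, SD (mg) | One t-test | ANOVA F-test | Combination vs one drug, Newman-Keuls | Combination vs both, Newman-Keuls |
|---|---|---|---|---|
| 15, 23 | 80.1% | 83.5% | 74.6% | 67.4% |
| 18.9, 23 | 94.2% | 96.3% | 92.6% | 89.5% |
| 15, 38 | 39.7% | 40.1% | 29.7% | 21.7% |
| 18.9, 38 | 57.1% | 59.1% | 47.8% | 38.5% |

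**Step 5: where the loss comes from.** Two unadjusted t-tests, both required to succeed, give 68.9% at 15 mg and SD 23. Most of the fall from 80% to 67% is therefore the need for two wins, not Newman-Keuls itself. At 18.9 mg and SD 23, requiring both costs about 5 points (94.2% to 89.5%). Moving the SD from 23 to 38 at 18.9 mg costs far more: 94.2% to 57.1% for one t-test.

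**The case against.** The best defence is that the plan over-provides on purpose. It expects at least a 30% reduction, says that it wants to be conservative, and takes the largest n in its table. Read as a lower bound, the closing statement is true: at SD 23, 38 per group detects 18.9 mg with more than 80% power, even when the combination must beat both drugs (89.5%). If about 10% were lost (an assumption, leaving 34 per group), that figure would still be about 85%. This stands. A reader might infer from the 67% that the trial is underpowered for its 30% target, or that needing two wins uses up the conservative margin. At SD 23 neither follows.

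Three further points also stand in part.

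- **No two-win rule is stated.** The section describes the sizing as a test for inequality among the three groups, and the F-test has 83.5% power even at 15 mg. The two-win reading is a reasonable inference from the objective and from the Background hypothesis of an effect greater than each drug alone, but it is not a documented criterion.
- **The figures concern opioid consumption only.** The Background makes pain the main hypothesis and opioid use the secondary one. For pain, at the text's 1.6-point difference and SD 2, power to beat both drugs at 38 per group is about 87%. The 67% must not be read as the power of the trial's main hypothesis.
- **The rank-based route may apply.** The plan itself suspects skewed data, in which case Kruskal-Wallis and Mann-Whitney would be used and the table above is only a guide.

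The low figures in the last two rows come from the SD, not from multiplicity.

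The defence does not rescue the sentence that at least 38 per group are needed for a 30% reduction, which the plan's own table contradicts. Nor does it supply power for the test that will be run.

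**Conclusion.** The point holds as a mislabelled effect and a mismatched test. At SD 23, 38 per group is the 80% sample size for 15 mg (22–24%) in one t-test. For the stated 30% (18.9 mg) the required number is 25, and the t-test power at 38 is 94%. Under ANOVA plus Newman-Keuls, power to beat both single drugs is about 67% at 15 mg and about 90% at 18.9 mg, assuming normal data, equal single-drug means and no dropout.

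The documents do not show a trial that is too small for its 30% target at SD 23. That reassurance depends on the SD. With the quoted ketamine SD of 38, 18.9 mg gives 57% for one t-test and about 38.5% for both. The percentages for 15 mg depend on whether 63 or 67 mg is the base, since the table leaves the group means blank. This is worth correcting because the sample size statement rests on it, but it is a correction to what is stated, not to the design.

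**What to change.** In Data Analysis:

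1. Name 15 mg (22–24% of 67 or 63 mg) at SD 23 as the effect for which 38 per group gives 80% power in a two-sample t-test. Say that the 30% difference of 18.9 mg needs 25 on the same basis.
2. Replace the claim of 80% power for a 30% reduction with the power of the planned procedure for the combination against each single drug and against both, at 15 and 18.9 mg, for SD 23 and for the quoted SD 38.
3. State the assumptions: normal data, equal single-drug means, no dropout. Add that the Kruskal-Wallis and Mann-Whitney route applies if the data are skewed, and that the figures concern opioid consumption, not pain.
4. Say whether the efficacy claim requires a significant difference from both single drugs, so that the reader knows which power figure applies.

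The cost is a short rewrite and one power calculation. Enrolment does not change. The drawback is a stated figure that looks less favourable at 15 mg and at SD 38.
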